### 12.1.4 Handling of Missing Values and of Values outside the Detection Limits

For BoExp parameters:

- Values below the lower limit of quantification (LLOQ) will be imputed using LLOQ/2. For values above the upper limit of quantification (ULOQ), the ULOQ will be imputed.
- The number of values below LLOQ or above ULOQ will be presented in each summary table. If more than 50% of the data are below LLOQ, only the number and percentage of values below LLOQ will be reported in the summary together with the minimum and maximum values.

For CASI data:

Subject missing the complete CASI will not be considered for analysis. Those with incomplete CASI's will be analyzed based on the available data.

Further details will be provided in the SAP.

### 12.1.5 Significance Level for Inferential Analysis

Not applicable as there are no formal statistical hypotheses to be tested in this study.

## 12.2 Determination of Sample Size

The sample size of a minimum of 169 participants in the Exposure and Non-Exposure Events Each is based on the expected exposure of a Non-Smoker when exposed to cigarette smoke as documented in the literature. Variability of exposure levels and method variability were furthermore considered to estimate the sample size needed.

---

## 12.3 Analysis Populations

The main population for analysis will be the Compliant Exposure Set.

### 12.3.1 Compliant Exposure Set

The Compliant Exposure Set will consist of all enrolled participants who have signed the ICF and who have participated in either a Non-exposure Event or an Exposure Event, have provided two urine samples (at minimum, one urine sample prior to the start of the event and one urine sample after a minimum 2h of individual participation in the event) and are compliant with the Event Exposure Groups (Non-Exposure vs. Passive Exposure).

### 12.3.2 Active Exposure Set

The Active Exposure Set (PP) will consist of all enrolled participants who have signed the ICF and who have participated in an Exposure Event, have provided two urine samples (at minimum, one urine sample prior to the start of the event and one urine sample after a minimum of 2h after start of the Active Exposure) and were in the Active Exposure Group.

## 12.4 Primary Analysis

The primary endpoints will be the pre-event urinary BoExp and latest post two hour urinary BoExp observation. A linear mixed effects model with event type, IAQ, duration of exposure (time between pre-event collection and last post exposure collection), product use status and product use status and event type interaction will be modelled as fixed effects with a random subject effect. Other covariates or interactions terms may be added as needed. Appropriate contrasts will be constructed to determine the effect of passive exposure to IQOS aerosol during the Exposure Event on the mean change in levels of urinary BoExp to selected tobacco specific HPHCs together with the 95% confidence intervals (CIs). Other contrasts can be constructed to determine the change in urinary BoExp for subjects with other smoking status after passive exposure to IQOS usage

## 12.5 Secondary Analysis

The same statistical model described in the analysis of the primary endpoint will be used to analyze to evaluate the levels of exposure to additional selected HPHCs representative of ETS during both the Non-Exposure Events and Exposure Events in the study population. The results will also be looked at stratified by incoming smoking status. Additional analysis may be defined in the SAP and performed and reported in the Assessment Study Report.

The IAQ data will be processed at the assessing laboratory (see Appendix B) and the individual results per compound will be summarized and tabulated. An Analysis of variance (ANOVA) design will be applied as the quantitative results of the IAQ sessions will be compared per compound. The mean, standard deviation, relative standard deviation,

---

### Confidentiality Statement

---

Data and information contained in this document are considered to constitute trade secrets and confidential commercial information, and the legal protections provided to such trade secrets and confidential information are hereby claimed under the provisions of applicable law. No part of this document may be publicly disclosed without the written consent of Philip Morris Products S.A

---

---

Related to PMI\_RD\_WKI\_000759

minimum and maximum will be computed per compound and the number of observation will be indicated. A significance level set at 0.05 will be used to determine equality between sessions.

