#### Confidentiality Statement

---

Data and information contained in this document are considered to constitute trade secrets and confidential commercial information, and the legal protections provided to such trade secrets and confidential information are hereby claimed under the provisions of applicable law. No part of this document may be publicly disclosed without the written consent of Philip Morris Products S.A.

---

---

Related to PMI\_RD\_WKI\_000759

1. Identification and consent of participants;
2. Non-Exposure dinner events ('Non-Exposure Event') of 4h duration for the individual participant where no use of any tobacco or nicotine-containing product is allowed, designed to establish background measurements in the absence of exposure to IQOS;
3. Exposure dinner Events ('Exposure Event') with 4h of exposure for the individual participants in the Passive Exposure Group, designed to measure BoExp to selected HPHCs representative of ETS in all participant groups.

A sufficient number of Non-Exposure Events and Exposure Events will be conducted depending on the size of the selected location and to ensure the following minimum number of participants in the respective groups:

Non-Exposure Event:

- Non-Exposed Group (no product use): a minimum of 169 participants comprised of Non-Smokers, IQOS-users not using IQOS or any other tobacco or nicotine-containing product and CC smokers not using the cigarettes or any other tobacco or nicotine-containing product for the duration of the Non-Exposure Event;

Exposure Event:

- Passive Exposure Group (no product use): a minimum of 169 participants passively exposed comprised of Non-Smokers, IQOS-users not using IQOS or any other tobacco or nicotine-containing product and CC smokers not using the cigarettes or any other tobacco or nicotine-containing product for the duration of the Exposure Event;
- Active Exposure Group (IQOS Use): 20% ± 5% of the available seats at the Event location of current IQOS Users using IQOS for the duration of the Exposure Event.

If necessary, additional Non-Exposure and Exposure Events might be conducted to achieve the necessary number of participants.

---

[figure not shown]

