8.2.2 Secondary Analysis of Indoor Air Quality Measurements

- Carbonyls: Acetaldehyde, Acrolein, Crotonaldehyde and Formaldehyde
 - At each event there are 3 suitcases sampling each sample at 1 hour intervals over 3 hours.
 - Each of the 9 observations will be used as the observations for the associated event.
- ISO measurement standards for ETS: 3-Ethenylpyridine (3-EP) and Nicotine
 - At each event there are 3 suitcases sampling 2 replicate samples at the end of the 3 hour interval.
 - Each of the 6 observations will be used as the observations for the associated event.
- Tobacco Specific Nitrosamines: NNN and NNK
 - At each event there are 3 suitcases sampling 2 replicate samples at the end of the 3 hour interval.
 - Each of the 6 observations will be used as the observations for the associated event.

- Real-time measurements of PM2.5 and PM10 suspended particles in air.
 - At each event there are 2 sensors measuring the suspended particulate matter a 1 minute interval monitoring.
 - For each sensors, the average of all readings will be calculated from the start till end of the event. These averages will be used as observations for that particular event.

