10 CHANGES FROM THE PROTOCOL SPECIFIED STATISTICAL ANALYSES

For the primary and secondary analysis, the random subject effect is removed as there are no repeated measures.

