12.6.2.1.1 Carbonyls

During each Exposure and Non-Exposure Event, there are 3 sampling cases that collects air for the assessment of carbonyls at 1 hour intervals. Each sampling case was placed at the same location during an Event.

The SAS procedure PROC MIXED will be used with the restricted maximum likelihood method for estimation of the parameters. The mixed model will have the carbonyl reading as dependent variable and the following covariates will be included in the model: Location, Event Number (Exposure Events 1-4 and Non-Exposure Event 1 and 2) and Event Type (Exposure and Non-Exposure Event). A repeated statement will be used to model repeated measures for the time variable.

The denominator degrees of freedom will be determined using the method of Kenward and Roger (1997). In case of non-convergence of the preferred model or memory space issues, the Kenward-Roger method will be replaced by Satterthwaite approximation.

The SAS code for the mixed model to be used is shown below:

```
Proc mixed data=_data_ method=reml;
Class location time event_type;
Model endpoint = location event type event num/ ddfm=kr;
Repeated time/subject=location(event num) type=cs;
Lsmeans event_type / diff alpha=0.05 cl;
Lsmeans location / diff alpha=0.05 cl;
Run;
```

The Geometric LS means and estimate of the ratio of geometric means between Exposure and Non-Exposure Events along with its 95% CI will be presented in tables for Formaldehyde, Acetaldehyde, Acrolein and Crotonaldehyde. The geometric LS means and ratio of geometric means together with their respective CIs are calculated by exponentiating the LSmeans and differences between exposures groups.

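### The protocol uses a 0.05 significance test with no margin to establish equal air quality between sessions, and the SAP drops this rule without recording the change

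*Protocol*

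**What the plan says.** Protocol 12.5, for the IAQ data: "An Analysis of variance (ANOVA) design will be applied as the quantitative results of the IAQ sessions will be compared per compound". It then gives the decision rule: "A significance level set at 0.05 will be used to determine equality between sessions". The synopsis repeats the rule under the processing and analysis of IAQ samples. Neither place gives a margin or says whether the unit of analysis is a reading or an event mean.

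Protocol 12.1.5, on the significance level for inferential analysis, reads: "Not applicable as there are no formal statistical hypotheses to be tested in this study".

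SAP 12.6.2.1.1 to 12.6.2.1.3 use mixed or linear models instead. For carbonyls, nicotine, 3-EP, NNN and NNK they report a ratio of geometric means, Exposure to Non-Exposure, with a 95% CI. For particulate matter the code requests the difference between event types with confidence limits, and SAP 12.6.2.1.4 exempts these values from log transformation. None of these sections contains an equality decision.

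SAP section 10, which lists changes from the protocol's analyses, has one entry: "the random subject effect is removed as there are no repeated measures".

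**The concern.** A significance test can return the answer 'equal' only by failing to reject. Without a margin, that outcome mixes two situations: the sessions really are alike, or the data are too few or too variable to show that they differ. IAQ is the first secondary objective, and Protocol 2.2 describes the study as intended to show that exposed Non-Smokers do not have higher biomarker levels. A rule that lets imprecision count as equality is therefore a poor one to leave in force.

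The documents also leave its status unclear. The protocol both sets a 0.05 level and says that none applies. The SAP drops the rule without saying so. Someone interpreting the air results with both documents in hand cannot tell whether p>0.05 may still be read as equality.

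**Working it through.** Neither document states a power, SD, margin or detectable difference for IAQ; the 169 participants concern the urinary biomarkers. There is no planned figure to reproduce, so the check asks how the written rule would behave.

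**Inputs from the documents**
- Two-sided level 0.05 (Protocol 12.5).
- Number of events. SAP 12.6.2.1.1 has "Event Number (Exposure Events 1-4 and Non-Exposure Event 1 and 2", so 2 versus 4. Protocol Table 5 has five events, apparently 2 versus 3. Protocol 4.1 leaves the number open: "If necessary, additional Non-Exposure and Exposure Events might be conducted to achieve the necessary number of participants".
- Readings per event (SAP 8.2.2). Carbonyls: "Each of the 9 observations will be used as the observations for the associated event". Nicotine and 3-EP, and likewise NNN and NNK: "Each of the 6 observations will be used as the observations for the associated event".

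**Assumptions, shown as ranges:** event-level log SD s of 0.1, 0.2 and 0.3; intraclass correlation ρ of readings within a session of 0.1, 0.3 and 0.5. The documents give neither.

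**Event as unit, 2 versus 4**
- SE = s × √(1/2 + 1/4) = 0.866s; df = 2 + 4 − 2 = 4; critical t = 2.776.
- Any observed difference below 2.776 × 0.866 = 2.40 SDs is declared equal.
- For a true difference of d SDs, power comes from the noncentral F(1, 4) with noncentrality (d/0.866)². It is 14.7% at d = 1 and 42.2% at d = 2, and reaches 80% at d = 3.26. So a true 1-SD difference is called equal 85% of the time and a 2-SD difference 58%.
- For a true 1.5-fold rise, d = ln 1.5 / s = 0.405 / s:

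| s | d | Called equal |
|---|---|---|
| 0.1 | 4.05 | 7% |
| 0.2 | 2.03 | 57% |
| 0.3 | 1.35 | 77% |

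With 2 versus 3 events (df = 3, critical t = 3.182, SE factor √(1/2 + 1/3) = 0.913), 80% power needs 3.89 SDs, and a true 2-SD difference is called equal 67% of the time.

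**Reading as unit, one-way ANOVA over 6 sessions with m readings each**
- With no product effect but normal session-to-session variation, the F statistic is distributed as [1 + mρ/(1 − ρ)] times a central F.
- m = 9: df 5 and 48, critical F 2.41. The multiplier is 2.0, 4.86 or 10.0 at ρ = 0.1, 0.3 or 0.5, so equality is rejected 32%, 78% or 94% of the time.
- m = 6: df 5 and 30, critical F 2.53. The multiplier is 1.67, 3.57 or 7.0, so equality is rejected 21%, 62% or 87% of the time.

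The nominal rate is 5%. The same rule therefore errs towards equality on one unit and against it on the other.

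**The case against.** The strongest objection concerns the test itself. The protocol compares sessions. A one-way ANOVA with session as the factor has no residual degrees of freedom on one mean per session, so it would have to use the readings, and the 2 versus 4 calculation is then for a different test. This stands. The event-level figures are conditional, and on readings the main risk runs the other way. The count of 2 versus 4 is also the SAP's, not the protocol's.

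Second, the event-level result depends on an SD that nobody has stated. At a log SD of 0.1, a 1.5-fold rise is detected 93% of the time. This stands too, and is why the low end is shown.

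Third, the SAP already reports estimates with CIs and has no equality rule. Protocol 12.1 leaves full detail to the SAP and promises that changes in method will be documented in the study report. This largely protects the planned estimates. It does not withdraw the protocol sentence, and SAP section 10 is the place where a reader would look for that.

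A reader might infer that the study will call large air-quality differences equal, or that it did. The documents do not support this. They leave the unit open, and the SAP sets no such decision. SAP 14.2 describes looking for the source of increased concentrations in indoor air, which is not an equality conclusion.

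**Conclusion.** The point holds as a fault in a protocol decision rule and in the record of its replacement. Concluding equality from a 0.05 test without a margin is invalid for any number of events, and the rule contradicts Protocol 12.1.5. SAP section 10 does not record that the ANOVA and its rule were dropped.

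The size depends on the unit and on assumed variation. If the event is the unit, a 1.5-fold rise would be missed between 7% and 77% of the time over log SDs of 0.1 to 0.3. If the reading is the unit, equality would be wrongly rejected between 21% and 94% of the time over ρ of 0.1 to 0.5. Neither use of the test can establish equality.

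The stronger claim, that few events make the planned analysis hide large differences, does not follow: the SAP's planned analysis has no equality rule. What remains at stake is how the air results may be interpreted and whether the change can be traced.

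**What to change.** 1. Delete the equality sentence from the synopsis and from Protocol 12.5. This also removes the conflict with 12.1.5.
2. State in its place that each compound is reported as the Exposure versus Non-Exposure estimate with the 95% CI already planned in the SAP. This is a ratio of geometric means for the carbonyls, nicotine, 3-EP, NNN and NNK. It is a mean difference for particulate matter, which is not log-transformed in the planned analysis.
3. Add that no equality between sessions or event types is concluded from p>0.05.
4. List the replacement of the ANOVA, and the withdrawal of its equality rule, in SAP section 10.

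The cost is protocol and SAP wording only, with no new data and no new analysis.

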#### 12.5.1 Analysis of the Active Exposure Group

The primary endpoints will look at the change between the pre-event urinary BoExp and latest post two-hour urinary BoExp observation. A linear mixed effects model with IAQ, duration of exposure (time between pre-event collection and last post exposure collection) and number of sticks used during the event, will be modelled as fixed effects with a random subject effect. Other covariates or interaction terms may be added as needed. Appropriate contrasts will be constructed to determine the effect of active exposure to IQOS usage during the Exposure Event on the mean change in levels of urinary BoExp to selected tobacco specific HPHCs together with the 95% confidence intervals (CIs).

---

## 13.2 Participant Confidentiality

All information obtained during the conduct of the study with respect to the participants' state of health will be regarded as confidential. A statement to this effect will be written in the information provided to the participant. An agreement to disclose any such information will be obtained from the participant in writing and signed electronically by the participant, in compliance with all local and national data protection and privacy legislation.

The anonymity of participants participating in this study will be maintained. Participants will be identifiable by the Sponsor (or Sponsor's authorized representative) on CRFs and other documents by their participant number/code, sex and date of birth, but not by name, initial, or

### Confidentiality Statement

---

Data and information contained in this document are considered to constitute trade secrets and confidential commercial information, and the legal protections provided to such trade secrets and confidential information are hereby claimed under the provisions of applicable law. No part of this document may be publicly disclosed without the written consent of Philip Morris Products S.A.

---

---

Related to PMI\_RD\_WKI\_000759

any other details relating to identifiable person (e.g., address). The assignment of a participant number/code for participant identification will be based on the appropriate data protection rules.

Any documents that allow full identification of the participant (e.g., the participant's signed ICF) must be maintained in confidence by the Principal Investigator. If any document relating to this study shows a participant's name or any other details relating to an identifiable person (e.g., address), the name or other identifiable details must be obscured before a copy of that document is supplied to the Sponsor. PRX staff will have access to email, geographical data and phone number as well as other personal data (i.e. passport check).

In the exceptional case where a participant a) is recruited into the study through PMP's Product Registration Database, and b) communicates in any way their intention to quit smoking or stop using IQOS, their email address will be shared with PMP so that this participant no longer receives any commercial communication from the Sponsor moving forward. No other identifiers will be shared with the Sponsor so that no study data will be linked to that email address.

### **13.3 Access to Source Documentation**

Participants enrolled in the study will be informed that, during the course of the study, the Sponsor, any authorized representatives of the Sponsor, IRB, or regulatory authorities may inspect the information collected, and ensure that all personal information made available for inspection is handled in the strictest confidence and in accordance with national and local data protection and privacy legislation.

The Principal Investigator and all study site collaborators involved with the study must permit direct access to source data/documents for study related monitoring, audits, IRB review, and regulatory inspection(s).

### **13.4 Record Retention**

All records of data, source data and source documents (original records or certified copies), in any form (including, but not limited to, written, electronic, magnetic, optical records and test results) that describe or record the methods, conduct, and/or results of the study, the factors affecting the study, and the actions taken will be maintained by the Principal Investigator for the study. After the finalization of the study the Principal Investigator can request that all study related files (Essential study documents/records, which individually and collectively permit evaluation of the conduct of a study and the quality of the data produced) are transferred to the Sponsor. The Sponsor will perform a quality control check for completeness of the data prior to accepting the request. Once the request is accepted and the transfer is complete, essential study documents/records, which individually and collectively

---

#### **Confidentiality Statement**

---

Data and information contained in this document are considered to constitute trade secrets and confidential commercial information, and the legal protections provided to such trade secrets and confidential information are hereby claimed under the provisions of applicable law. No part of this document may be publicly disclosed without the written consent of Philip Morris Products S.A.

---

---

Related to PMI\_RD\_WKI\_000759

permit evaluation of the conduct of a study and the quality of the data produced must be retained by the Sponsor for a minimum of:

- At least 15 years after completion or discontinuation of the study, or
- At least 2 years depending on, for example, the circumstances, or
- After formal discontinuation of clinical development of the IP.

These documents should be retained for a longer period, however, if required by the applicable regulatory requirements or by an agreement with the Sponsor.

Examples of essential records/documents include, but are not limited to:

- Signed informed consent documents for all participants and master ICF
- Participant identification code list, enrollment log (if applicable)
- Record of all communications between the Principal Investigator and the IRB, composition of the IRB
- Record of all communications/contact between the Principal Investigator, Sponsor, and its authorized representatives
- Study specific questionnaires (and associated data/scoring), CASI data
- All other source documents (e.g., laboratory records) or any electronically captured study source data
- Record of any body fluids or tissue samples collected and retained
- Information regarding participants' discontinuation.

The Principal Investigator (until transfer to the Sponsor is complete) and the Sponsor (after completion of the transfer) must take measures to prevent accidental or premature destruction of these documents.

If the Principal Investigator wishes to assign the study records to another party or move them to another location during or after the study, the Sponsor must be notified in advance.

The Principal Investigator must obtain written approval from the Sponsor before destruction of any records. Normally, these records will be held in the Principal Investigator's archives. If the Principal Investigator is unable to meet this obligation, they must ask the Sponsor for permission to make alternative arrangements. Details of these arrangements must be documented. In case the Principal Investigator has agreed with the Sponsor to transfer the files to the Sponsor it is the obligation of the Sponsor to document the destruction of the records according to local law and regulations.

The Sponsor or Sponsor's authorized representative will maintain documentation relating to the study for 15 years after the Study Report has been finalized.

